## **2.5 DATA HANDLING CONVENTIONS**

### **2.5.1 General conventions**

The following formulas will be used for computation of parameters.

#### **2.5.1.1 Duration of the study**

The duration of the study is computed in days as follows:

$$\text{Maximum (Visit dates, Termination date)} - \text{minimum (Date of V1)} + 1$$

#### **2.5.1.2 Subject Duration**

The duration of a subject participation in the trial is computed as follows:

$$\text{Maximum (Date of visits, termination date)} - \text{Date of V1} + 1$$

### **2.5.1.3 Time interval**

The time interval between two visits/vaccinations/blood samples is computed as follows:

Later date – earlier date.

### **2.5.1.4 Influenza vaccination during the previous influenza season**

This information will be used as collected. No derivation or imputation will be done.

## **2.5.2 Data handling conventions for safety variables**

### **2.5.2.1 Solicited reactions**

#### **Daily intensity:**

All daily records for solicited reactions will be derived into daily intensity according to the following classification: None, Grade 1, Grade 2, Grade 3, or Missing. The category of Unknown will be considered Missing if Unknown is recorded.

For measurable injection site reactions (Erythema/Swelling/Induration/Bruising):

- Grade 1:  $\geq 25$  to  $\leq 50$  mm
- Grade 2:  $\geq 51$  to  $\leq 100$  mm
- Grade 3:  $> 100$  mm

For measurable systemic reactions (Fever):

- Grade 1:  $\geq 38.0$  to  $\leq 38.4$  °C, or  $\geq 100.4$  to  $\leq 101.1$  °F
- Grade 2:  $\geq 38.5$  to  $\leq 38.9$  °C, or  $\geq 101.2$  to  $\leq 102.0$  °F
- Grade 3:  $\geq 39.0$  °C, or  $\geq 102.1$  °F

For the derivation of daily intensities the following sequential steps will be applied:

For solicited reactions (except Fever/Pyrexia) with an investigator presence recorded as “No” and with all daily records missing, all daily intensities will be derived as “None”.

For non-measurable solicited reactions, daily intensities will correspond to daily records reported in the clinical database. For measurable solicited reactions the daily measurements reported in the clinical database will be converted based upon the intensity scales defined in the protocol; this assumes a reaction that is too large to measure (non-measurable, “NM”) is Grade 3. Note that the intensity could be considered as “None” (not a reaction) in the analysis despite being considered a reaction by the investigator (e.g., swelling measurement  $> 0$  mm but  $< 25$  mm in adults).

Note: The maximum intensity during the ongoing period is derived from the record of the maximum intensity/measurement after the end of the solicited period following the rule described above.

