**Maximum intensity:**

Maximum intensity is derived from the daily intensities computed as described in above “Daily intensity” and is calculated as the maximum of the daily intensities over the period considered. The Grade of intensity is applied following the rules described in Section 9.1.3.2 of the protocol.

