**Presence:**

Presence is derived from the maximum intensity of the period considered:

- No presence : None
- Presence : Grade 1, Grade 2 or Grade 3
- Unknown or Missing presence : Missing

Subjects with at least one non-missing presence for a specific endpoint will be included in the analysis. Conversely, those without a non-missing presence will not be included in the analysis of the endpoint.

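### SAP 2.5.2.1 keeps an investigator 'No' without daily records as a non-reactor but drops an investigator 'Yes' without daily grades, which can only lower the reported incidence of the five non-measurable solicited reactions

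*SAP*

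**What the plan says.** SAP 2.5.2.1 (Solicited reactions) derives each subject's result in steps.

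- **Daily intensity.** The rule opens "For solicited reactions (except Fever/Pyrexia", so fever is set aside. For the other nine reactions "with an investigator presence recorded as “No” and with all daily records missing, all daily intensities will be derived as “None". This is the only step that uses the investigator's presence answer to fill a gap.
- **Non-measurable reactions.** "For non-measurable solicited reactions, daily intensities will correspond to daily records reported in the clinical database". Nothing is provided for the case where the investigator records a reaction but no daily record exists.
- **Size-graded reactions.** A measurement above 0 but below 25 mm is analysed as None ("not a reaction) in the analysis despite being considered a reaction by the investigator").
- **Maximum intensity.** It "is calculated as the maximum of the daily intensities over the period considered". The text does not say how a Missing day enters that maximum.
- **Presence.** "Presence is derived from the maximum intensity of the period considered". A Missing maximum gives a Missing presence, and "those without a non-missing presence will not be included in the analysis of the endpoint".

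SAP 2.5.4 leaves subjects with missing data out of percentages unless otherwise specified. For missing solicited intensities it only refers back to the Daily intensity rule.

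**The concern.** Take two subjects with the same empty record for, say, headache. If the investigator recorded 'No', the subject counts as a non-event. If the investigator recorded 'Yes', the subject disappears from the endpoint. Whether a subject is analysed then depends on the outcome being measured.

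Solicited reactions from D0 to D7 are a main part of the safety description, and describing safety is one of the study's two stated objectives. The affected results are the incidence rates and their Clopper-Pearson intervals. No hypothesis is tested, so no p-value is involved.

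The SAP handles comparable gaps differently elsewhere. An unsolicited non-serious AE is an event once it has a verbatim term (2.5.2.2), its missing intensity stays missing (2.5.4), and the maximum-intensity summary has a Missing category (2.4.4.1). Missing causality is counted as related (2.5.4), and a reaction too large to measure is taken as Grade 3 (2.5.2.1). Losing a confirmed reactor does not fit that pattern.

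**Working it through.** The documents give no reaction rate and no frequency of missing daily records, so there is no planned figure to reproduce. All counts below other than the group size are assumptions.

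**Inputs.** N = 55 per Cohort 2 group (SAP 1.3). Let a = subjects with a recorded Grade 1 to 3, m = subjects with investigator 'Yes' and no daily grade, and k = how many of those m would truly be Grade 1 or higher. Intervals are Clopper-Pearson (SAP 2.5.8.3).

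**Formulas.** The SAP rate is a/(N − m). The full-data rate is (a + k)/N. The shortfall is

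(a + k)/N − a/(N − m) = [k(N − m) − am] / [N(N − m)].

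The SAP rate is therefore too low when k/m > a/(N − m), and too high when k/m < a/(N − m).

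**Step 1: the five non-measurable reactions.** The intensity scale has no level below Grade 1, so a genuine 'Yes' is taken as at least Grade 1 and k = m. The shortfall becomes m(N − a − m) / [N(N − m)]. It is never negative, because a + m cannot exceed N. Enumerating every a and m for N = 55 and N = 60 found no exception.

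| Counting 'Yes' as present | SAP, m = 1 | SAP, m = 2 | SAP, m = 3 |
|---|---|---|---|
| 3/55 = 5.5% | 2/54 = 3.7% | 1/53 = 1.9% | 0/52 = 0.0% |
| 6/55 = 10.9% | 5/54 = 9.3% | 4/53 = 7.5% | 3/52 = 5.8% |
| 17/55 = 30.9% | 16/54 = 29.6% | 15/53 = 28.3% | 14/52 = 26.9% |
| 28/55 = 50.9% | 27/54 = 50.0% | 26/53 = 49.1% | 25/52 = 48.1% |

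One lost reactor costs 0.9 to 1.8 points. Three cost 2.8 to 5.5 points. As an example of the intervals, 17/55 has 19.1 to 44.8% and 14/52 has 15.6 to 41.0%.

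**Step 2: the four size-graded reactions.** Here an ungraded 'Yes' may be under 25 mm, so k can be smaller than m. With a = 14 and m = 3 the SAP gives 14/52 = 26.9%.

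| k | Full-data rate | SAP minus full-data |
|---|---|---|
| 0 | 14/55 = 25.5% | +1.5 points |
| 1 | 15/55 = 27.3% | −0.3 |
| 2 | 16/55 = 29.1% | −2.2 |
| 3 | 17/55 = 30.9% | −4.0 |

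The sign depends on k, which is unknown.

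**Step 3: is the 'No' rule itself the fault?** Take 3 graded reactors, 3 'Yes' and 4 'No' without records, N = 55. Under the SAP the rate is 3/52 = 5.8%. Dropping both kinds gives 3/48 = 6.25%. Using both answers gives 6/55 = 10.9%. Most of the gap comes from not using 'Yes'. Keeping confirmed non-reactors is right.

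**Step 4: partly missing records.** If Missing days are ignored in the maximum, a non-measurable reaction with 'Yes', some days None and the rest missing is tabulated as absent. Each such subject costs 1/55 = 1.8 points. This rests on a reading that the SAP does not state.

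**The case against.** Four arguments count against the point.

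1. **It should be rare.** Staff review the diary at Visit 2 (protocol 5.1.4) and clarify incomplete entries at interview (11.1). Missing diary data are clarified verbally and transferred to the CRB (13.2), and queries follow (11.2). This stands, and the effect is probably small. However, the SAP has a rule for fully missing records with 'No', so such records are foreseen. An interview may also establish that a reaction occurred without recovering daily grades.
2. **It stays visible.** Reactions left out of the analysis are listed (SAP 2.4.4.1), and numbers missing are shown when relevant (2.5.4). This is true, but a listing does not correct a rate or its interval.
3. **The analysis is descriptive and the intervals are wide.** This is also true: the intervals in Step 1 overlap heavily. The descriptive rates are nevertheless the safety result.
4. **The direction is not general.** This stands fully for the size-graded reactions, as Step 2 shows.

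A reader might infer that every solicited reaction rate can only be biased down. The documents do not support that: the 25 mm rule allows an upward shift for four reactions, and fever is outside the 'No' rule.

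A reader might also infer that the arm with more reactors is understated most. That is not general. With true incidence p and a share s of reactors lost, the absolute shortfall is ps(1 − p)/(1 − ps). At s = 10% it is 2.6 points at p = 50%, 1.7 at 80% and 1.0 at 90%. The relative shortfall, s(1 − p)/(1 − ps), falls as p rises.

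**Conclusion.** The concern holds for pain, headache, malaise, myalgia and shivering. Followed as written, the SAP keeps confirmed non-reactors without daily records and removes confirmed reactors without daily grades, so the reported incidence of these five can only be lowered. The size is about 1 to 2 points per lost reactor at 55 per group.

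This rests on two assumptions: that an investigator 'Yes' means at least Grade 1 within the solicited period, and that such records occur at all, since the documents give no frequency. For erythema, swelling, induration and bruising the handling is equally one-sided but the direction of the error is unknown. For fever the asymmetry does not arise. It is a modest defect, but it lies in a stated rule and is cheap to correct before the key code is released.

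**What to change.** - **Five non-measurable reactions.** In SAP 2.5.2.1, Presence, add for pain, headache, malaise, myalgia and shivering only: if investigator presence is 'Yes', no Grade 1 to 3 is recorded and at least one daily record is missing, then presence is Yes and maximum intensity is Missing. This also settles the partly missing case.
- **Tables.** Add a Missing row to the solicited maximum-intensity tables in 2.4.4.1, as the unsolicited tables already have.
- **Four size-graded reactions.** For 'Yes' with all daily measurements missing, report the number per group and add a sensitivity analysis counting these subjects as present.
- **Leave unchanged** the size and temperature thresholds and the fever handling. The Presence rule should not be extended to measured reactions: swelling of 10 mm on seven days with one day blank would then count as a reaction, against the SAP's own grading.

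The cost is a few lines of SAP text and a little programming, with no new data collection. Reported reaction rates may become slightly less favourable.

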**Maximum intensity:**

Maximum intensity is derived from the daily intensities computed as described in above “Daily intensity” and is calculated as the maximum of the daily intensities over the period considered. The Grade of intensity is applied following the rules described in Section 9.1.3.2 of the protocol.

**Presence:**

Presence is derived from the maximum intensity of the period considered:

- No presence : None
- Presence : Grade 1, Grade 2 or Grade 3
- Unknown or Missing presence : Missing

Subjects with at least one non-missing presence for a specific endpoint will be included in the analysis. Conversely, those without a non-missing presence will not be included in the analysis of the endpoint.

**Time of onset:**

Time of onset is derived from the daily intensities computed as described above in “Daily intensity”. It corresponds to the first day with intensity of Grade 1, Grade 2, or Grade 3.

Note: If a reaction is not continuous (i.e., reaction occurs over two separate periods of time intervened by at least one daily intensity Missing or None) then the time of onset is the first day of the first occurrence.

**Table 4 – Categories for time of onset**

Injection Site Reactions (D0-D7)	Systemic Reactions (D0-D7)
D0-D3	D0-D3
D4-D7	D4-D7

**Number of days of occurrence:**

Number of days of occurrence over the period considered is derived from the daily intensities computed as described above in “Daily intensity”. It corresponds to the number of days with daily intensities of Grade 1, Grade 2, or Grade 3. Number of days of occurrence on the solicited period with a specified intensity may also be derived.

**Table 5 – Categories for number of days of occurrence during the solicited period**

Injection Site Reactions (D0-D7)	Systemic Reactions (D0-D7)
1-3 days	1-3 days
4-7 days	4-7 days
8 days	8 days

**Overall number of days of occurrence:**

If a reaction is ongoing at the end of the solicited period, then the overall number of days of occurrence is derived from the daily intensities and the stop date of the reaction after the end of the solicited period. The overall number of days of occurrence is:

$$\begin{aligned}
 & (\text{stop date} - \text{vaccination date}) \\
 & + (\text{number of days of occurrence within the solicited period}) \\
 & - \text{length of the solicited period} + 1
 \end{aligned}$$

If the stop date is missing or incomplete (containing missing data [MD]), the overall number of days of occurrence will be considered as Missing.

**Table 6 – Categories for overall number of days of occurrence**

Injection Site Reactions	Systemic Reactions
1-3 days	1-3 days
4-7 days	4-7 days
≥8 days	≥8 days
Missing	Missing

**Ongoing:**

Ongoing is derived from the last daily intensity of the solicited period computed as described above in “Daily intensity” and the maximum intensity on the ongoing period. The investigator’s ongoing flag is not used because the measurement would determine the ongoing status of the reaction.

Note: a reaction could be derived as not ongoing for the analysis despite being considered as ongoing by the investigator (e.g. when the maximum measurement after D7 for adults aged ≥65 years is >0 mm but <25 mm). If the last daily intensity of the solicited period is at least Grade 1 and maximum intensity on the ongoing period is also at least Grade 1, then the reaction is considered ongoing. In any other cases the reaction will not be considered as ongoing.

### **2.5.2.2 Unsolicited non-serious AEs**

Unsolicited AEs include non-serious unsolicited AEs and SAEs. This subsection only covers the endpoints for unsolicited non-serious AEs.

#### **Presence:**

An observation will be considered an event if it has at least a verbatim term.

#### **Intensity:**

Intensity for unsolicited non-serious AE will be derived according to the following classification: None, Grade 1, Grade 2, Grade 3, or Missing.

If the unsolicited non-serious AE is measurable and its preferred term is part of the list of solicited reactions, then the measurement is derived based upon and following the same rule as the intensity scales defined in the protocol for that measurable injection site or systemic reaction.

Note that the intensity could be considered as “None” (not a reaction) in the analysis despite being considered a reaction by the investigator (e.g., swelling measurement >0 mm but <25 mm). Intensity for the other unsolicited non-serious AEs will correspond to the value reported in the electronic case report form (eCRF).

The maximum intensity corresponds to the highest intensity for a unique term.

#### **Time of onset:**

Time of onset is derived from the start date of the unsolicited non-serious AE provided in the clinical database and the date of last vaccination:

Start date of the unsolicited non-serious AE – date of vaccination.

The time of onset should be considered as missing only if one or both of the dates are missing or partially missing.

The unsolicited non-serious AEs will be analyzed “Within 28 days”, which corresponds to AEs with a time of onset between 0 and 28 days after vaccination or missing. An AE with missing time of onset will be considered to have occurred just after the vaccination indicated by the visit number, so will be included in these tables.

Note: Unsolicited non-serious AE that occurred before vaccination (negative time of onset) or with a time of onset higher than defined above (>28 days) will not be included in analysis, but will be listed separately.

Time of onset will be displayed as follows:

- D0-D3
- D4-D7

- D8-D14
- $\geq$ D15
- Missing

**Duration:**

Duration is derived from the start and stop dates of the unsolicited non-serious AE provided in the clinical database:

Stop date of unsolicited non-serious AE – start date of unsolicited non-serious AE + 1.

The duration should be considered as missing only if one or both of the start and stop dates of the unsolicited non-serious AE is missing or partially missing.

Duration will be displayed by period as following:

- 1-3 days
- 4-7 days
- 8-14 days
- $\geq$ 15 days
- Missing

**2.5.2.3 Serious adverse events**

**Time of onset:**

Time of onset will be computed using the same methodology than for unsolicited non-serious AEs described in [Section 2.5.2.2](#).

SAEs will be analyzed throughout the study using the following periods:

- Within 28 days after vaccine injection
- During the whole study (i.e., all SAEs occurred during the study)

An SAE with missing time of onset will be considered to have occurred just after the vaccination indicated by the visit number, but will be listed separately.

**Duration:**

Duration will be computed using the same methodology than for unsolicited non-serious AEs described in [Section 2.5.2.2](#).

**Intensity:**

The intensity for SAE will be computed using the same methodology than for unsolicited non-serious AEs described in [Section 2.5.2.2](#).

#### **2.5.2.4 Other safety endpoints**

##### **Action taken:**

This information will be summarized as collected, including missing observations. No derivation or imputation will be done.

##### **Seriousness:**

This information will be summarized as collected for SAE. No derivation or imputation will be done.

##### **Outcome:**

This information will be summarized as collected. No derivation or imputation will be done.

##### **Causality:**

This information will be summarized as collected. An adverse reaction (AR) is defined as an unsolicited non-serious AE or an SAE with causality to the vaccine. Missing causality (relationship) will be handled as described in [Section 2.5.4](#).

##### **AEs leading to study discontinuation:**

A flag is available in the clinical database for all AEs in order to identify AEs leading to discontinuation.

In general, the items that are counted are:

- Disposition table: A subject who has, on the termination form, the reason for early termination “adverse event” is checked.
- Safety overview table: A subject who has either on the termination form, the reason for early termination “adverse event” is checked or lists an AE on an AE page (solicited, unsolicited, or SAE) that has “Reaction Leading to Termination” or “Event Leading to Termination” or “Serious Adverse Event Leading to Termination” checked that is at least Grade 1 and is within the time period indicated. Note: If the Grade is below 1, the AE will be excluded from the list of AEs leading to study discontinuation.
- System organ class (SOC)/Preferred term (PT) table: An event (solicited, unsolicited, or SAE) that has “Cause Study Termination” or “Caused Study Discontinuation” checked that is at least Grade 1 and is within the time period indicated.

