#### ***Handling of missing intensity adverse events***

For solicited reactions, missing intensities will be handled as described in “Daily intensity” of [Section 2.5.2.1](#). For unsolicited non-serious AEs, missing intensities will remain missing and will not be imputed.

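### The SOC/PT table and the list of AEs leading to discontinuation drop an investigator-flagged event graded below 1 (read literally, also one with a missing grade) and can disagree with disposition and overview

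*SAP*

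**What the plan says.** SAP 2.5.2.4 (AEs leading to study discontinuation) sets a separate rule for each table.

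- Disposition: "Disposition table: A subject who has, on the termination form, the reason for early termination" is recorded as adverse event. No grade is required.
- Safety overview: "Safety overview table: A subject who has either on the termination form, the reason for early termination" is adverse event, or who has an AE-page termination flag "checked that is at least Grade 1 and is within the time period indicated". The note attached to this rule reads "If the Grade is below 1, the AE will be excluded from the list of AEs leading to study discontinuation".
- SOC/PT table: only a flagged event (solicited, unsolicited or SAE) that is at least Grade 1 and in the period. The termination form is not a route in.

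Grades below 1 and missing grades can both occur. SAP 2.5.2.2 states: "Intensity for unsolicited non-serious AE will be derived according to the following classification: None, Grade 1, Grade 2, Grade 3, or Missing". A measurable reaction below the scale is derived as 'None' "despite being considered a reaction by the investigator (e.g., swelling measurement >0 mm but <25 mm"). SAP 2.5.2.3 derives SAE intensity by the same method. For unsolicited non-serious AEs, SAP 2.5.4 says "missing intensities will remain missing and will not be imputed".

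Protocol 9.1.2 and SAP 2.1.4 include early termination in the endpoints for solicited reactions, unsolicited AEs and SAEs, and neither sets a minimum grade. SAP 2.4.4.1 plans a summary of all, and of related, AEs leading to discontinuation within 28 days. SAP 2.5.2.2 (Presence) counts an unsolicited observation as an event once it has a verbatim term.

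**The concern.** Whether an event ended participation is the investigator's judgement, recorded by a flag. The SAP then overrides that flag with a derived grade that measures something else. Of the three tables, only SOC/PT names the event; disposition and overview count subjects. An event dropped from SOC/PT therefore leaves a subject shown as discontinued for an AE with no corresponding preferred term in the table meant to supply it.

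For unsolicited AEs the rule also departs from the SAP's own conventions. An ungraded event counts as present on its verbatim term, and SAP 2.4.4.1 gives 'Missing' its own row in the intensity summary. Yet the same event fails the Grade 1 condition in the discontinuation table. Missing causality, by contrast, is handled conservatively in SAP 2.5.4: it is analysed as related.

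At stake is a small safety count in a purely descriptive study, where what readers see is whether the table shows such an event or none.

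**Working it through.** The plan gives no figure on this point, so there is none to reproduce. The check applies the three rules of SAP 2.5.2.4 to one subject with one in-period AE, varying the termination-form reason, the AE-page flag and the derived grade.

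- Disposition = 1 if the form says adverse event.
- Overview = 1 if the form says adverse event, or if the flag is yes and the grade is at least 1.
- SOC/PT = 1 if the flag is yes and the grade is at least 1.

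| Form reason | Flag | Grade | Disposition | Overview | SOC/PT |
|---|---|---|---|---|---|
| AE | yes | ≥1 | 1 | 1 | 1 |
| AE | yes | None | 1 | 1 | 0 |
| AE | yes | Missing (literal reading) | 1 | 1 | 0 |
| not AE | yes | ≥1 | 0 | 1 | 1 |
| not AE | yes | None, or Missing (literal reading) | 0 | 0 | 0 |
| AE | no | any | 1 | 1 | 0 |

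Reading the table:

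1. The grade condition always removes a flagged event graded 'None' from SOC/PT and never changes disposition.
2. It removes the subject from the overview only in the fifth row, where the form and the AE page disagree.
3. The fourth and sixth rows show differences that have nothing to do with grade. They arise because the tables use different sources, so removing the grade condition would not make the tables agree in every case.

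Size, as an illustration that assumes one affected subject. Group size is 55 (SAP 1.3, Cohort 2), with Clopper-Pearson limits as in SAP 2.5.8.3.

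- With the filter, 0/55 = 0%. Upper limit 1 − 0.025^(1/55) = 6.49%; interval 0 to 6.49%.
- Without it, 1/55 = 1.82%. Lower limit 1 − 0.975^(1/55) = 0.05%; upper limit, the 97.5th percentile of Beta(2, 54), = 9.72%.
- For a QIV-HD group with both cohorts combined (55 + 5 = 60), the entry moves from 0% (0 to 5.96%) to 1/60 = 1.67% (0.04 to 8.94%).

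**The case against.** The strongest reply is that the subject is rarely lost. Protocol 5.2.10 has the most significant reason checked and lists adverse event first; Protocol 5.2.8 has a voluntary withdrawal for safety concerns recorded as an adverse event. The form should therefore normally say so, which keeps the subject in disposition and overview. This stands. A reader might infer that such discontinuations vanish from all the discontinuation tables; the documents do not support that.

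The missing-grade limb is an inference. The note speaks only of grades below 1, and the SAP never says how a missing grade is treated here. It fails the Grade 1 condition only on a literal reading. Such cases should also be uncommon, since missing information must be explained (Protocol 11.1) and queries closed before lock (Protocol 13.4.1). This stands as a limit on frequency, but the silence still needs filling.

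The below-1 route is narrow: a measurable reaction under 25 mm, or a temperature under 38.0°C. Other AEs keep their recorded grade. This stands.

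For solicited reactions, the filter follows the SAP's convention. SAP 2.5.2.1 treats intensity 'None' as "not a reaction) in the analysis despite being considered a reaction by the investigator" and derives it as no presence. Counting such a reaction as a cause of discontinuation would contradict the solicited tables. This stands for solicited reactions. It does not carry over to unsolicited AEs, whose presence rule does not depend on grade.

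Finally, information survives elsewhere. Solicited-reaction listings show early termination (SAP 2.4.4.1), and discontinued subjects are listed with reasons tabulated by group (SAP 2.2). This is partly an answer: SAP 2.4.4.1 makes no matching statement about early termination for the unsolicited AE listings, and a listing does not correct a table count.

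**Conclusion.** The point holds for the SOC/PT table and the list of AEs leading to discontinuation. By stated rule they omit a flagged event whose derived grade is below 1 and, read literally, an unsolicited AE or SAE whose grade is missing. This conflicts with an endpoint that has no grade threshold and with a planned summary of all such AEs. For unsolicited AEs it also conflicts with the presence rule.

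The usual result is 1/1/0 across disposition, overview and SOC/PT. It becomes 0/0/0 only if the termination form also fails to give adverse event as the reason.

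The effect is small. Few events are expected, and the movement from 0% to 1.8% rests on one assumed event in a group of 55. No hypothesis test is affected, because none is planned. This is a minor correction worth making before database lock, not a threat to the safety conclusions.

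**What to change.** In SAP 2.5.2.4:

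- For unsolicited AEs and SAEs, remove the Grade 1 condition from the overview and SOC/PT rules, and remove the note. Count every flagged event within the stated time period and show its grade as derived, including 'None' and 'Missing'.
- For solicited reactions derived as 'None', choose one treatment in advance: count them with a footnote that the solicited tables show them as not present, or keep the exclusion and footnote any flagged reaction left out.
- Footnote that disposition and overview draw on different sources, so their counts may still differ.

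The cost is a few words in the SAP and one program filter. The count may rise, and if flagged solicited reactions derived as 'None' are counted there is a small inconsistency with the solicited tables, which the footnote explains.
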